7.4.3 Method for Assigning Subject to Treatment Groups

This is an observational study and not a randomized trial.

7.4.4 Subject Compliance Monitoring

All pertinent procedures and data collection will occur in the operating room. Subject compliance monitoring is not applicable for this study.

7.4.5 Blinding of the Test Article

There is no blinding involved in this study.

7.4.6 Receiving, Storage, Dispensing and Return

7.4.6.1 Receipt of Test Article

ICG will be transported from the Investigational Drug Services (IDS) pharmacy to the OR pharmacy the day before surgery or the morning of the surgery depending on when the surgery is scheduled at HMC, Vasser Brother's Medical Center, or Emory University School of Medicine. The ICG will come in a 25mg vial with 10 mL of Ampule (Solvent). Subjects will receive 2.25 mg of indocyanine green (ICG) in a volume of 0.9 mL.

7.4.6.2 Storage

The ICG will be stored in the IDS pharmacy at HMC, Vasser Brother's Medical Center, or Emory University School of Medicine until the day before surgery or the morning before surgery if it is scheduled for the afternoon. A copy of the

consent form for each patient will be sent to IDS pharmacy at HMC, Vasser Brother's Medical Center, or Emory University School of Medicine prior to surgery. ICG should be stored at room temperature (between 20 – 25 degrees Celsius).

7.4.6.3 Preparation and Dispensing

The ICG will be brought from IDS pharmacy at HMC, Vasser Brother's Medical Center, or Emory University School of Medicine to the OR pharmacy the day before surgery so it is available for use the next day. If the surgery is scheduled for the afternoon then IDS pharmacy may bring the ICG over on the morning of surgery, not the day before. The surgeon will prepare the ICG and solvent for injection in the operating room prior to the start of the procedure. All aspects of the ICG preparation and use will be handled by the surgeon. Once reconstituted the ICG can be used for up to six hours, making it possible to use in several different cases in one day if the doses are drawn up in a sterile environment at the same time.

7.4.6.4 Return or Destruction of the Test Article

Any remaining ICG will be discarded in the OR at HMC, Vasser Brother's Medical Center, or Emory University School of Medicine.

7.4.6.5 Prior and Concomitant Therapy

NA

8.0 Subject Numbers and Statistical Plan

8.1 Number of Subjects

A total of 40 subjects will be recruited into this study (we estimate we will enroll 20 subjects from Penn State Hershey Medical Center and 20 between Vasser Brother's Medical Center and Emory University School of Medicine.).

The learning curve for sentinel node biopsy is 5 cases. In order to insure that the data collected accurately represents the effectiveness of the SPY machine, each surgeon will have the goal of enrolling at least 8 subjects into the study.

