1.2 Primary Study Endpoints

The primary endpoint is the number of sentinel nodes correctly identified with ICG and fluorescence imaging alone.

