2.0 Background

1.1 Scientific Background and Gaps

Sentinel node biopsy is a routine procedure in patients with both melanoma and breast cancer. The status of the sentinel node provides prognostic information and guides further treatment options in these patients. Sentinel node biopsy (SLN) was first developed using only a blue dye. Technetium99, a radioactive protein, was added later and provides the ability to image the patient and identify relevant lymph node basins. This feature is particularly important for trunk melanomas that can drain to multiple nodal basins. For the last 15 years or so, the standard method of SLN localization includes both tech99 and blue dye. While the rates of localization overall are excellent, these methods each have drawbacks.

Technetium 99 (tech99) is a radioactive protein that is injected dermally around the melanoma or the areola of the breast, usually one day prior to surgery. Lymphoscintigraphy is done 1-2 hours after injection and identifies the nodal basin that contains the sentinel node. Tech99 has an excellent track record of identifying sentinel nodes, but it does involve an extra trip to the hospital (patients are injected the day prior to surgery), the injection is often the most painful part of the entire treatment experience, and the signal can be vague and difficult to localize in the operating room. Furthermore, there are international concerns about the reliability of the supply of radio-labelled colloid. The reactors that currently provide tech99 and other radioactive substances are aging, and shortages of material have been threatened in the past.

Blue dye is injected dermally on the day of surgery, after the patient is anesthetized. This is a visual adjunct to the radioactive signal from the tech99. These two methods together have a success rate of approximately 96% in identifying the sentinel node. Blue dye alone localizes about 50% of sentinel nodes, and it can be problematic for the surgeon in that it stains tissues and is toxic to skin grafts.

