8.3 Statistical methods

The analysis of these results will be descriptive. We will assess the number of nodes per patient that are correctly identified with ICG alone, and the number of patients in whom ICG was successfully used

alone. Multiple surgeons will be involved, some with more experience than others with this technique. We will assess the learning curve by studying the success rate with ICG over time for each surgeon.

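### Given the 5-case learning curve in 8.1 and the unclear training wording in 10.1, does section 8.3 need a separate study-level result for later cases?

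*Combined protocol and SAP*

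**What the plan says.** Three parts of the protocol bear on this.

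- **Section 8.1** plans 40 subjects, about 20 at Hershey and 20 across the other two sites. It states "The learning curve for sentinel node biopsy is 5 cases" and then sets a target, worded as "each surgeon will have the goal of enrolling at least 8 subjects into the study". The purpose it gives for that target is "In order to insure that the data collected accurately represents the effectiveness of the SPY machine".
- **Sections 1.2 and 8.3** give the endpoint and its analysis. The endpoint: "The primary endpoint is the number of sentinel nodes correctly identified with ICG and fluorescence imaging alone". The analysis is descriptive: "We will assess the number of nodes per patient that are correctly identified with ICG alone", together with the count of patients in whom ICG alone succeeded. Section 8.3 then acknowledges "Multiple surgeons will be involved, some with more experience than others with this technique" and, as its response to that difference between surgeons, plans the following: "We will assess the learning curve by studying the success rate with ICG over time for each surgeon".
- **Sections 10.1, 16.5 and 18.5** describe surgeon training. Section 10.1 has collaborating surgeons monitored over a minimum of three subjects or until proficient, and also has proficiency judged before a surgeon starts enrolling. Section 16.5 speaks of three surgeries and 18.5 of at least three cases; neither says whether those patients are in the study.

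Section 7.1 calls the study an observational pilot, and 8.2 calls the sample size one of convenience.

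**The concern.** Section 8.1 treats learning as a threat to the meaning of the data: a goal of 8 subjects against a 5-case curve makes sense only if cases after the fifth tell us something the first five do not. Section 8.3 does not carry that into a study-level figure. The headline count and success rate mix early and later cases, and the per-surgeon trend is thin. A surgeon new to ICG who enrols exactly 8 subjects has only 3 after the fifth.

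The wording of 10.1 adds to this. If subjects there means enrolled participants, its usual sense in the protocol, some of the 40 would be supervised training cases. If proficiency is settled before enrolment, none would be. If early cases do worse, the all-case rate would understate what ICG alone achieves in practised hands.

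**Working it through.** **The plan's own figure.** N = 40 has no formula behind it, and 8.2 gives no power, target rate or precision. What can be checked is consistent: 20 + 20 = 40, and 40/8 = 5, so at most five surgeons can all meet the goal of 8.

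**Per-surgeon precision.** With no failures, the exact 95% lower limit is 0.025^(1/n).
- 3 of 3: 29.2%
- 5 of 5: 47.8%
- 8 of 8: 63.1%

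Per-surgeon results are therefore descriptive only, which is all 8.3 claims for them.

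**Possible size of the pooling effect.** The documents give neither the number of surgeons nor how many are new to ICG, so these are assumptions. Let k be the number of new surgeons and t the ICG cases each completes before enrolling.
- Early cases = k × (5 − t)
- Share = early cases / 40
- Later rate minus pooled rate = share × (later rate − early rate)

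The later rate is assumed to be 96%. The Background section gives that figure only for tech99 plus blue dye: "These two methods together have a success rate of approximately 96% in identifying the sentinel node". Early rates of 90% and 80% are assumptions too.

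| New surgeons, prior ICG cases | Early cases | Share | Gap, early rate 90% | Gap, early rate 80% | Later cases | Lower limit, no failures |
|---|---|---|---|---|---|---|
| any, 5 | 0 | 0% | 0 | 0 | 40 | 91.2% |
| 2, 3 | 4 | 10% | 0.6 | 1.6 | 36 | 90.3% |
| 3, 3 | 6 | 15% | 0.9 | 2.4 | 34 | 89.7% |
| 2, 0 | 10 | 25% | 1.5 | 4.0 | 30 | 88.4% |
| 3, 0 | 15 | 37.5% | 2.25 | 6.0 | 25 | 86.3% |
| 5, 0 | 25 | 62.5% | 3.75 | 10.0 | 15 | 78.2% |

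Gaps are in percentage points; one patient in 40 is 2.5 points. The last row needs five surgeons, none past the curve. That fits poorly with 8.3, which says some surgeons have more experience with the technique, and with the PI's completed ICG trial described in the Background. For scale, 39 successes in 40 has an exact 95% interval of 86.8% to 99.9%, which is 13.1 points wide.

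**Reading 10.1.** The passage describes observation as training and places the proficiency judgement before enrolment. Section 16.5 gives proper training as the purpose of the three observed surgeries. Section 15.1 mentions charges when ICG is used in patients outside the study, so such use is contemplated. Read together, these give a coherent sequence: observe, judge proficiency, then enrol, with subjects used loosely. On the other reading, at three observed cases each, 2 × 3 = 6 or 3 × 3 = 9 of the 40 would be training cases. Even that count is not fixed, because 10.1 ties the number to proficiency.

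**What is analysed.** Section 8.1 recruits 40, 7.2.2 requires a data form for each case, and 8.3 excludes no one. The all-case summary covers the same 40 subjects on either reading.

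**The case for a change.** The best case for a change is that the protocol itself raises learning, and that 8.2 wants a sample from which conclusions about the technique can be drawn. Performance after learning is part of such a conclusion. Pooled later cases would be far more informative than per-surgeon fragments: 25 of 25 has a lower limit of 86.3%, against 29.2% for 3 of 3. A cut chosen after seeing the data is open to selection, and fixing it now costs only a table.

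Much of this stands as fact. Section 8.3 names no pooled split, 10.1 is loosely worded, and 16.5 and 18.5 do not settle it. It is also fair to say that the direction of any effect is not guaranteed, since an observer might help early cases succeed.

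It does not follow that the plan must change. The proposed cut rests on a 5-case figure stated for sentinel node biopsy, and 16.2 says all the surgeons already perform that routinely; applying it to ICG is an inference. Fixing the cut in advance would not make it the right one, and it would cost precision. The trend over time that 8.3 already promises orders cases by surgeon, so an early-versus-later count can be drawn from the same data wherever earlier ICG experience is known. Whether the data form records that experience cannot be checked, because the form was uploaded separately.

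**Conclusion.** No change is needed. The plan as written gives a sound descriptive result: an all-case summary of 40 subjects, with learning described surgeon by surgeon. The missing pooled split is a supplement that analysts can add, and the wording of 10.1 is unclear rather than contradictory. It could be tidied alongside 16.5 and 18.5, with any observed cases among the 40 flagged, but the all-case summary does not depend on it.

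For two or three surgeons assumed new to ICG, the effect on the pooled rate is 0.6 to 2.4 points if three training cases come before enrolment, less than one patient in 40, and 1.5 to 6.0 points if none do. It is zero if learning is complete before enrolment. These figures depend on assumed surgeon numbers and success rates. If early cases do worse, the bias runs against ICG, and no test, threshold or stated number in the plan would alter.

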8.2 Sample size determination

Sample size of convenience. This is a feasibility study, and is intended to determine if fluorescence lymphangiography can be used alone to localize sentinel nodes in patients with melanoma or breast cancer. The sample size of 40 subjects is our estimation of an appropriate number of subjects such that we can draw conclusions about this technique for sentinel node biopsy, and allows sufficient numbers for multiple surgeons to be involved.

8.3 Statistical methods

The analysis of these results will be descriptive. We will assess the number of nodes per patient that are correctly identified with ICG alone, and the number of patients in whom ICG was successfully used

alone. Multiple surgeons will be involved, some with more experience than others with this technique. We will assess the learning curve by studying the success rate with ICG over time for each surgeon.

9.0 Confidentiality, Privacy and Data Management

See the attached Research Data Plan form (HRP-598)

10.0 Data and Safety Monitoring Plan

10.1 Periodic evaluation of data

Collaborating surgeons will be monitored for at least 3 subjects, or until they demonstrate proficiency with ICG and the SPY device. Proficiency of each surgeon will be assessed by the PI or a representative from Stryker prior to each surgeon enrolling patients. While observing the collaborating surgeons for training purposes, the PI or a representative from Stryker will look for competence in and understanding of the use of the SPY machine. Each surgeon should demonstrate an understanding of the images that they are looking at on the SPY machine during the procedure. After 10 subjects, the PI will review the cases to insure that sentinel nodes are being identified for each subject.

10.2 Data that are reviewed

Any adverse events that occur during surgery, whether deemed related to the ICG or not, will be reviewed. Adverse events will include reactions to ICG such as hives. Efficacy will be determined by success rates of localizing sentinel nodes with ICG alone.

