1.3 Secondary Study Endpoints

Secondary endpoints include adverse events related to ICG and operative time for sentinel node biopsy.

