3.3 Early Withdrawal of Subjects

3.3.1 Criteria for removal from study

Subjects will be removed from the study if they withdraw consent prior to surgery. The study itself occurs only in the operating room, with no long term follow-up or involvement of the subject.

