7.4.2 Treatment Regimen

The patient will receive a dermal injection of indocyanine green (ICG) 0.9 mL at the melanoma tumor site or subareola if breast cancer while they are in the operating room under general anesthesia. This is a one-time injection so no dose adjustments will be made.

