10.3 Method of collection of safety information

Safety information will be collected from the collaborating surgeons, through case report forms.

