10.4 Frequency of data collection

Safety data collection starts when the patient signs informed consent. Data will be collected on the day of surgery, on the standardized data collection form which is separately uploaded. Data should be forwarded to the PI within 7 business days of collection. Adverse events should be reported within 7 business days.

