10.5 Individuals reviewing the data

Data will be reviewed by the PI. Adverse reactions to ICG are extremely rare, and have occurred with higher doses of ICG in subjects undergoing retinal angiography. No adverse reactions were seen in the prior study with 87 subjects, and none have been reported in the literature concerning sentinel node biopsy with ICG.

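### ICG-related adverse events are a secondary endpoint, but the stated review covers events during surgery; later reactions such as headache count only if noticed or volunteered

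*Combined protocol and SAP*

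**What the plan says.** Section 1.3 reads: "Secondary endpoints include adverse events related to ICG and operative time for sentinel node biopsy".

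The rules for finding these events are in section 10. Section 10.2 states the review: "Any adverse events that occur during surgery, whether deemed related to the ICG or not, will be reviewed". Its next sentence gives hives as an example of an ICG reaction and sets no time limit. Section 10.3 names the source: "Safety information will be collected from the collaborating surgeons, through case report forms". Section 10.4 starts safety collection at consent and adds: "Data will be collected on the day of surgery, on the standardized data collection form which is separately uploaded". It gives no end to the period.

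Section 11.0 lists three rare ICG reactions: anaphylaxis, urticaria and headache. Section 7.4.2 has the injection given "while they are in the operating room under general anesthesia", whereas section 7.2.2 allows the subject to be either sedated or anesthetized.

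Section 19.1 defines an adverse event with no surgical limit. Section 18.4 sends all adverse events to the PI within seven days, and section 19.2 follows those observed or reported and thought to be associated with the drug or device. The planned analysis in section 8.3 is descriptive and does not mention adverse events.

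**The concern.** The endpoint and the stated way of finding its events do not cover the same period. The endpoint has no time limit. The review rule in section 10.2 stops with the operation, and the source is the surgeon's form. A site that follows that rule to the letter would leave one listed reaction, headache, to chance reporting, along with any hives that first show in recovery.

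The expected result is close to zero events. If zero is recorded, a reader will want to know whether nothing happened or nobody looked after the operating room. With three sites and several surgeons, sections 10.2 and 10.4 could also be read differently from place to place, so the counts might not cover the same period.

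**Working it through.** **Step 1. The stated windows side by side.**

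| Section | Period or route | Is the subject checked after surgery? |
|---|---|---|
| 10.2 | Events during surgery | No |
| 10.3 | Surgeons' case report forms | Not stated |
| 10.4 | From consent; collected on the day of surgery; no end | Not stated; recovery not excluded |
| 18.4 | All events to the PI within seven days | No; acts once an event is known |
| 19.1, 19.2 | Definition has no surgical limit; events observed or reported are followed | No; passive |
| 19.4.1 | Observed or volunteered events that are serious, unexpected and suspected reactions | No; would not apply to a non-serious headache |
| 20.1.2 | PI confirms that events are correctly entered | No; acts on recorded events |

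No section describes an active check after the operation.

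**Step 2. The listed reactions against the section 10.2 window.** Anaphylaxis and urticaria can be seen during surgery. Hives that first appear afterwards fall outside it. Headache depends on the subject saying so, which is not possible under general anesthesia and depends on the depth of sedation otherwise.

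**Step 3. What a count from 40 subjects can show.** The plan gives no figure to reproduce: the 40 subjects are a convenience sample (section 8.2) and no safety analysis is specified. Counting subjects with at least one event, the exact (Clopper-Pearson) two-sided 95% upper limits are:

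- 0/40: 1 − 0.025^(1/40) = 0.0881, or 8.8%.
- 1/40: the p that solves (1−p)^40 + 40p(1−p)^39 = 0.025, which is 0.1316, or 13.2%.
- 2/40: the same with 780p²(1−p)^38 added on the left, which gives 0.1692, or 16.9%.

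So one missed subject moves the reported limit from 8.8% to 13.2%, and two move it to 16.9%. This shows how sensitive the limit is. It is not evidence that anyone is missed.

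**Step 4. Chance of recording none when capture is incomplete.** Let p be the true reaction rate and c the share of reactions that the process picks up. The documents give neither, so both are assumed over a range. P(none recorded) = (1 − pc)^40.

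| Assumed p | c = 1 | c = 0.5 | c = 0.25 |
|---|---|---|---|
| 1% | 67% | 82% | 90% |
| 2.5% | 36% | 60% | 78% |
| 5% | 13% | 36% | 60% |

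For example, at p = 5% and c = 0.5: (1 − 0.025)^40 = 0.363.

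**Step 5. The prior trial.** Section 10.5 says: "No adverse reactions were seen in the prior study with 87 subjects". The upper limit is 1 − 0.025^(1/87) = 0.0415, or 4.2%; with the 89 enrolled according to section 2.1 it is 1 − 0.025^(1/89) = 0.0406, or 4.1%. The documents do not say how or until when that trial looked for events, so this result does not settle whether late reactions occur.

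**The case against.** A reader might infer that the plan confines safety data to the operating room and so shuts out later events. Two sentences invite this. Section 7.4.4 says "All pertinent procedures and data collection will occur in the operating room", and section 3.3.1 says "The study itself occurs only in the operating room, with no long term follow-up or involvement of the subject". Neither is a safety-window rule. The first explains why compliance monitoring does not apply. The second stands under criteria for removal and disclaims long-term follow-up, which is not the same as same-day recovery. Section 7.3 counts the operative visit as participation, which is arguably wider than the operating room. Section 10.4 does not exclude recovery, and sections 18.4, 19.1, 19.2, 19.4.1 and 20.1.2 leave a later event countable once it is known. The stronger reading fails.

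A second inference would be that events will in fact be missed. The documents do not show that either. The data collection form was uploaded separately and was not available for this review; it may have a recovery field, in which case only wording needs changing. A subject who is sedated, as section 7.2.2 allows, may be able to speak.

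It could also be said that section 10.7 rules out any summary of safety. It calls statistical analysis not meaningful, under a heading about tests in the monitoring plan. That does not prevent a descriptive count, and section 8.3 plans description. Finally, an exact limit in a pilot of this size is good practice rather than a necessity.

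What remains is narrower. The one sentence that defines which events are reviewed stops at surgery, the wider sentence has no end, and every route for later events is passive.

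**Conclusion.** The point holds in limited form. As written, section 10.2 reviews events during surgery, while the endpoint includes a reaction that an anesthetized subject cannot report. Later events may be counted, but only if noticed or volunteered, so a zero would be hard to interpret.

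The size of any undercount cannot be derived from the documents and may be zero. The limits and probabilities above illustrate sensitivity under assumed rates and capture shares. The conclusion rests on the stated text, without sight of the data collection form. Severity is low: this is a cheap improvement to a secondary endpoint, and the count of sentinel nodes identified with ICG is untouched.

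**What to change.** 1. In sections 10.2 and 10.4, replace the limit to events in surgery with a counting window for this endpoint: from ICG injection through discharge from recovery. The start of safety collection at consent can stay.
2. State that the site investigator checks the existing recovery record for events in that window. That such a record is available at all three sites is an assumption to confirm. If the data collection form already has a recovery field, align the wording to it.
3. In section 8.3, add that all events in the window are reported and, separately, those judged related under section 19.3. Count subjects with at least one event and give an exact two-sided 95% upper limit (8.8% for 0/40), stated to apply to that window.
4. Leave sections 18.4 and 19.2 unrestricted. Tying them to discharge from recovery could narrow safety reporting that is now open-ended. Sections 3.3.1 and 7.4.4 need no change.

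The cost is about 40 short chart checks and a few sentences of text, with no added visit or procedure. There are two drawbacks. Non-specific post-operative events such as headache cannot all be attributed to ICG without a control arm. And a chart holds only what recovery staff saw or asked about, so the check narrows the gap without closing it.

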1.0 Objectives

1.1 Study Objectives

The objective of this study is to determine if fluorescence lymphangiography can be used alone to localize sentinel nodes in patients with melanoma or breast cancer. The hypothesis is that sentinel nodes can be identified using only indocyanine green (ICG) and fluorescence lymphangiography, without the need for technetium99 and a gamma probe.

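### The primary endpoint counts the nodes ICG finds but has no term for those it misses, and the patient-level success measure that could answer the question is undefined and unranked

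*Combined protocol and SAP*

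**What the plan says.** Section 1.1 states a hypothesis without a performance level: "The hypothesis is that sentinel nodes can be identified using only indocyanine green (ICG) and fluorescence lymphangiography". Section 8.2 says the study "is intended to determine if fluorescence lymphangiography can be used alone to localize sentinel nodes in patients with melanoma or breast cancer".

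The measures meant to answer this appear in three places:

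- Section 1.2: "The primary endpoint is the number of sentinel nodes correctly identified with ICG and fluorescence imaging alone". This is a count and has no denominator.
- Section 8.3: "The analysis of these results will be descriptive". It then lists two measures. One is based on nodes: "We will assess the number of nodes per patient that are correctly identified with ICG alone". The other is at patient level and concerns use of ICG on its own: "the number of patients in whom ICG was successfully used". It does not rank them or say what makes a use successful.
- Section 10.2, in the data and safety monitoring plan: "Efficacy will be determined by success rates of localizing sentinel nodes with ICG alone". It does not say whether the rate is per node or per patient.

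Section 7.2.2 fixes what is counted. Every fluorescent node is resected and treated as sentinel, including one with no gamma signal. The gamma probe is then used on the open basin, and any gamma-positive node found there is removed and imaged. If fluorescence finds nothing within 30 minutes, the surgeon changes to the gamma probe.

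**The concern.** The study exists to learn whether the gamma probe can be left out. The informative failures are a gamma-positive node still in the basin after the ICG dissection, and a subject in whom ICG finds nothing. The design collects both, but the primary endpoint uses neither. A missed node simply adds nothing to the count, and an extra gamma-negative fluorescent node can make up for it.

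Success in 8.3 could mean that at least one node was found, or that none was missed. These are different claims about ICG alone, and the choice between them is open until the data are in. A summary resting on the count or the at-least-one rate could look complete while a material share of subjects had a node that only the gamma probe found.

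**Working it through.** The plan has no figure to reproduce. Section 8.2 calls the 40 subjects a convenience sample, and no target rate or interval is given.

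**Inputs from the protocol.** 40 subjects (8.1); a mean of 1.89 sentinel nodes per patient with tech99 in the earlier trial (2.1 Previous Data); the counting rule in 7.2.2. Expected gamma-positive nodes: 40 × 1.89 = 75.6, taken as 76.

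**Assumed.** The number of missed nodes, how they fall across subjects, and the number of gamma-negative fluorescent nodes.

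**Step 1. How each event enters each measure.**

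| Event | Count (1.2) | At least one node found | Every node found |
|---|---|---|---|
| Gamma-positive node found by ICG | +1 | success | success if no other node is missed |
| Gamma-negative fluorescent node | +1 | success | does not offset a miss |
| Gamma-positive node missed, another node found by ICG | 0 | success | failure |
| No node found by ICG | 0 | failure | failure |

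Only the last column registers both kinds of failure.

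**Step 2. Example.** ICG misses 6 of 76 nodes, in 6 different subjects who each have another ICG-found node. Intervals are exact (Clopper-Pearson).

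- Gamma-positive nodes found: 76 − 6 = 70; 70/76 = 92.1% (95% CI 84% to 97%, ignoring clustering within subject).
- Subjects with at least one node found: 40/40 = 100% (91% to 100%).
- Subjects with no node missed: (40 − 6)/40 = 34/40 = 85.0% (70% to 94%).
- Mean ICG count: 70/40 = 1.75. With 6 gamma-negative fluorescent nodes added, (70 + 6)/40 = 1.90, close to the earlier trial's tech99 mean of 1.89, although the 6 misses remain.

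**Step 3. Other numbers of misses, one per subject, each subject having another ICG-found node.**

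| Missed | Node level | At least one | No node missed (exact 95% CI) |
|---|---|---|---|
| 4 | 72/76 = 94.7% | 40/40 | 36/40 = 90.0% (76% to 97%) |
| 6 | 70/76 = 92.1% | 40/40 | 34/40 = 85.0% (70% to 94%) |
| 8 | 68/76 = 89.5% | 40/40 | 32/40 = 80.0% (64% to 91%) |

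**Step 4. When the gap closes.** If the same 6 misses are both nodes of 3 two-node subjects, and ICG finds nothing else in them, both patient-level measures are 37/40 = 92.5% (80% to 98%).

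**Step 5. Misses independent within subject.** Take 36 subjects with 2 nodes and 4 with 1 (36 × 2 + 4 = 76) and node sensitivity s.

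- Every node found: (4s + 36s²)/40 = 81.9% at s = 0.90 and 92.5% at s = 0.96.
- At least one found: (4s + 36[1 − (1 − s)²])/40 = 98.1% and 99.5%.

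**The case against.** The strongest reply is that this is a declared observational pilot with a convenience sample and a descriptive analysis. Section 1.2 names one primary endpoint, and 1.3 lists the secondary endpoints separately. Section 8.3 commits to assessing both nodes per patient and patient-level success, so a reader of the report would see much of any divergence. Every subject still receives tech99 as backup.

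Most of this stands. The lack of a powered test is not an error, and a binding pass mark is not something this design must have. What the reply does not mend is that the named primary endpoint has no term for a missed node, and that success in 8.3 is undefined. Reporting both 8.3 measures helps only if the patient-level one has a fixed meaning.

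Two stronger readings are tempting.

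- A reader might infer that 1.2 and 10.2 contradict each other. The text does not establish this. Section 10.2 describes what is reviewed during monitoring, and its rates may be the rate form of the node count in 1.2. The fault there is a missing unit.
- A reader might set the 85% in the example against the roughly 96% success quoted in the scientific background and conclude that ICG alone fell short. The 96% refers to tech99 plus blue dye. It is not described as the proportion of patients with every node found, and the plan does not adopt it as a benchmark, so the comparison is not supported.

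**Conclusion.** The concern holds as a gap in how the endpoint is defined. As written, the primary count cannot register a gamma-positive node that ICG missed, and the patient-level measure that could do so has no definition or rank. The question posed in 1.1 and 8.2 therefore has no fixed measure that answers it.

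With 4 to 8 misses in separate subjects who each have another ICG-found node, the two meanings of patient-level success differ by 10 to 20 percentage points. With independent misses at node sensitivity 90% to 96%, they differ by about 7 to 16 points. The gap is zero if misses occur only in subjects in whom ICG finds nothing. These sizes rest on assumed misses and on about 76 gamma-positive nodes. The gap in definition does not depend on them.

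A reader might also infer that the investigators intend to choose the flattering measure, or that dropping tech99 will follow from this study. Neither is in the documents: 8.3 commits to both measures, and 12.2 says only that a suitable group of patients may be defined.

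**What to change.** - **1.2 and 8.3:** make the deciding measure the proportion of subjects in whom ICG alone found every sentinel node before the gamma probe was used. Count as a failure any subject with a gamma-positive node left in the basin at the gamma check, and any subject in whom ICG found no node. Report it with an exact 95% CI.
- **8.3:** label node counts, nodes per patient and per-surgeon rates over time as supportive.
- **10.2:** use the same measure and state its unit.
- **Before enrolment:** state how the proportion and its interval will be read against the hypothesis in 1.1. Any benchmark is the sponsor's choice, with its source given.

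This is a wording change. It adds no subjects or procedures, and 7.2.2 already generates the observations needed; the data collection form, which is not among these documents, should be checked for whether each node was found before or after the gamma probe was used. The cost is that the stated result may look less favourable than a node count or an at-least-one-node rate, and that its interval at 40 subjects will be wide (70% to 94% in the example).
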